- i) Approval letters from all the IRB of record for all participating sites (or indicate that they are pending and provide upon receipt): UCLA IRB approved this study on 13 JAN 2014. UCLA IRB# 13-001670
- j) Confirm that the PI at GLA will maintain documentation of all correspondence between participating sites and their IRBs of record:

The Principal Investigator for both UCLA and VA GLA, [name], will maintain documentation of all correspondence between participating sites and their IRBs of record for UCLA, VA GLA and the Department of Defense/USAMRAA.

10. Subject Population

We plan to enroll a total of 74 subjects for this study. We will identify the 74 subjects from the VA GLA Healthcare System who are currently in treatment and have received treatment-asusual (TAU) for the last 3 months in the PTSD Clinic or the Domiciliary Care Program. TAU may consist of medication and/or group psychotherapy. In addition to TAU, Veterans who have begun a structured, evidence-based therapy such as cognitive behavior therapy (CBT), cognitive processing therapy (CPT), or Prolonged Exposure (PE) therapy at least 6 weeks prior to beginning the study, and who continue to receive therapy, may also be eligible. Subjects will be enrolled into an eight-week treatment protocol in which they will be assigned to one of two treatment groups: 1) active TNS plus TAU; or 2) sham TNS plus TAU. Study activities will be performed at the VA GLA and the Semel Institute at the University of California, Los Angeles.

Participants will be recruited as described below from the PTSD Clinic ([name], LCSW, Director) and the Domiciliary Care Program ([name]., Director) of the VA GLA Healthcare System.

PTSD Clinic:

The PTSD Clinic caseload includes over 1,800 veterans with PTSD, including approximately 400 veterans from Iraq or Afghanistan (OIF/OEF/OND). The clinic receives an average of 25 referrals a week

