Potential subjects who are referred by clinic staff will speak with the study coordinator who will provide information (goal of the study, treatment conditions, risks and benefits of participating, use of double-blind random assignment, time commitment, compensation for participation, and schedule of payments) allowing them to decide whether they want to participate. Staff will make clear to the subjects that their participation in the study is strictly voluntary and that their refusal to participate in the study will in no way prejudice their ongoing care in the PTSD Clinic or Domiciliary Care Program. Those who are interested will have an appointment scheduled. All participants will receive a copy of the Subject's Bill of Rights prior to discussions of consent to participate. Discussions will take place in a private office to ensure the confidentiality of the discussions and safeguard the privacy of the participants. The consent form outlines procedures, potential risks and anticipated benefits, right to withdraw, and confidentiality; it will be read with each participant, allowing time for questions. The research coordinator will review the consent form to ensure that all subjects comprehend the requirements and procedures of the study, and will ask the potential subjects questions about the protocol after they have explained it to ensure that they truly comprehend the nature and procedures of the study. All potential participants will be offered time to decide if they want to participate and the opportunity to take a copy of the consent form home to read and discuss with family or friends before giving their consent. When subjects are prepared to consent, they will review the procedures of the study with one of the coinvestigators who will obtain the subjects' consent. Participants who qualify after passing screening will be randomized as a subject to a treatment condition. Those who do not pass

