Following the baseline assessment, subjects then will be randomized to one of the two treatment conditions. Treatment assignment will be randomized within cells defined by gender, symptom severity, and presence of current medication treatment to provide a degree of balance on key underlying characteristics that otherwise would have the potential to confound the interpretation of study findings. Specifically, there will be eight strata for randomization defined by the 2 x 2 x 2 combinations of gender (male or female), symptom severity (lower or higher defined by whether the CAPS-5 score on entry is less than 78, the median value for this sample, versus being 78 or greater), and presence of current medication treatment (yes or no). Within these strata, randomization will occur in blocks of two, so that after every two patients with a given combination of stratum-defining characteristics, there will be one patient assigned to the active intervention and one to the control arm. The randomization will be carried out by associating strata with rows of the random-number table in Cochran (1977, p. 19). For the first member of each successive pair of patients presenting with a given set of stratum-defining characteristics, if the next number in the row is in the range of 5 through 9, then the patient will be assigned the active intervention, else the patient will be assigned to the sham. If the first subject was assigned the active intervention, then the next subject would be assigned the sham, and vice versa; for the next subject after that, the random-number table will be used in the same way. The pairing in the design could be considered in the analysis, and we will plan to do so using a permutation-test approach for purposes of being complete. The core motivation for the pairing, however, is to ensure that treatment assignment remains balanced across arms rather than because we believe that there is anything scientifically important about whether the subject arrives at an odd or an even number in the sequence. For our primary analysis, we will use a randomized-block ANOVA that accounts for the 2 x 2 x 2 stratification in the design but does not reduce the error degrees of freedom on account of the pairing.

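### Assignments are read from a published random-number table with a printed decoding rule and fixed blocks of two, and no procedure is described that keeps the sequence concealed before entry

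*Combined protocol and SAP*

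**What the plan says.** The randomization paragraph in Section 13 (Methods and Procedures, conduct of the study) states that "there will be eight strata for randomization defined by the 2 x 2 x 2 combinations of gender", symptom severity (CAPS-5 below 78, or 78 and above) and current medication. It continues: "Within these strata, randomization will occur in blocks of two".

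On the source of the sequence it says: "The randomization will be carried out by associating strata with rows of the random-number table in" a published work, identified by source, year (1977) and page (19). The rule for the first of each pair is printed: "if the next number in the row is in the range of 5 through 9, then the patient will be assigned the active intervention", and otherwise sham. The second follows from the first: "If the first subject was assigned the active intervention, then the next subject would be assigned the sham, and vice versa". On the link between table and strata, the text says only "associating strata with rows". It does not say which row goes with which stratum or where in a row reading begins.

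The Section 13 overview blinds subjects and the research staff who meet them, and has a UCLA staff member without subject contact program the devices. Section 11 describes consent: when subjects are ready, "they will review the procedures of the study with one of the coinvestigators who will obtain the subjects' consent". Section 13 also provides that subjects who do not enter the extension are told their arm after their follow-up visits, 12 weeks in total. Section 7 gives the trial phase 36 months.

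**The concern.** Blinding protects an assignment after it has been made. Concealment keeps the next assignment unknown until a subject has been irrevocably entered. The plan covers the first. In the text available it does not say who links rows to strata, who reads the table, or how an assignment is withheld until entry.

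A public table makes this gap matter more. With an undisclosed list, learning past arms says nothing about the first member of the next pair. With a published page and a printed rule, each known arm helps to show which row is in use, and the row then gives every later assignment in that stratum.

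There is also room to act on such knowledge. Attending physicians of the PTSD Clinic are co-investigators and coordinate referrals, and co-investigators obtain consent. One stratum factor is an interviewer-rated score cut at 78, recorded before randomization. Selective entry, or scoring near the cut, would bias the comparison. The stratified ANOVA does not correct for that, and the planned permutation test takes assignment to be unpredictable at entry.

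**Working it through.** **Inputs.** From the documents: N = 74 ("We plan to enroll a total of 74 subjects for this study"), 37 per arm, eight strata, blocks of two, digits 5 to 9 active, unblinding after 12 weeks, trial phase of 36 months. Assumed: R usable rows on the page, R = 8 to 20, because the table is not reproduced.

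**1. The plan's own figure.** P(active) = 5/10 = 0.5, and 74 × 0.5 = 37 per arm, as stated. This is an expectation. If all eight strata end on an unpaired patient, the split can reach 41/33.

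**2. What the fixed block gives away.** If u strata end unpaired, (74 − u)/2 assignments are second in a pair and fixed by the first.
- u = 0: 37 of 74 (50%). Best-guess rate (37 + 37/2)/74 = 75%.
- u = 8: 33 of 74 (45%). Best-guess rate (33 + 41/2)/74 = 72%.

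Simple randomization gives 50%. These rates require the earlier member's arm to be known.

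**3. What the protocol text alone gives away.** Taking one row per stratum, the number of possible row-to-stratum links is R!/(R − 8)!: 40,320 for R = 8 and about 5.1 × 10⁹ for R = 20. The printed text does not fix the sequence.

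**4. How fast the link can be inferred.** Each revealed pair halves the candidate rows, so about log₂R pairs are needed: 3.0 for R = 8 and 4.3 for R = 20. This is a rough threshold. After m pairs, (R − 1)/2^m wrong rows still fit on average: 7/8 = 0.9 for R = 8 and m = 3; 19/16 = 1.2 for R = 20 and m = 4. It also takes the starting position as known. S equally likely starts would add log₂S pairs, for example 3.3 for S = 10.

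**5. Simulated guessing** (five pairs per stratum, page in hand, link unknown, start known):

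| | R = 8 | R = 20 |
|---|---|---|
| Past arms seen | 88.5% | 84.6% |
| Past arms not seen | 63.0% | 58.7% |

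When past arms are seen, the second of each pair is always right. The rate for the first of the pair is therefore 2 × 0.885 − 1 = 77% for R = 8 and 2 × 0.846 − 1 = 69% for R = 20. An undisclosed list with the same blocks would leave it at 50%.

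**6. Whether arms become known in time.** Twelve weeks is about 2.8 months. If the last subject's 12 weeks fall inside the 36-month phase, enrolment can run for at most 36 − 2.8 = 33.2 months. With equal strata, 74/8 = 9.25 subjects per stratum, or one every 33.2/9.25 = 3.6 months, longer than the 2.8 months to unblinding. The documents state no accrual rate, so equal strata and steady entry over the whole window are assumptions. Faster accrual or larger strata would shorten the gap.

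**The case against.** A reader might infer that the whole sequence is open to anyone holding the protocol and the cited page, or that all 74 arms are settled before a subject is met. The documents do not support this. The row link and starting position are not printed. A subject's stratum is also not fixed until the baseline CAPS-5 is scored, which follows consent, so even someone with the link cannot tie an arm to a person with certainty before then. Some foresight is still possible earlier. If gender and medication are known, two strata remain, and their next assignments agree with probability 0.5² + 0.5² = 0.5, in which case the arm is known whatever the score.

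A reader might equally infer that allocation is unconcealed. That also goes too far. The overview states that contact staff, who would include the consenting co-investigators and the coordinator, are blinded to assignment. The supportable statement is that no concealment procedure for the sequence is described. Some pages were not available to this review, and the Section 9(c) list of institutional roles breaks off after the VA entry. If a list-holder is named there, that part of the point falls away.

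The best counter-argument is that a secret row link and a secret computer seed both depend on custody. That is right about custody, but the two are not equivalent: the row can be worked out from a handful of revealed arms, whereas an undisclosed list gives no such lead on later blocks.

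Inference has limits too. Extension participants stay blinded, so only some arms emerge. Someone must also know the order of entry within a stratum and connect it to the page.

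**Conclusion.** The point holds as a weakness in the stated method. The sequence comes from a public source with a printed rule and disclosed blocks of two, and the available text names neither a list-holder nor a release step. Whoever sets, learns or infers the row link and start can foresee later assignments in a stratum once a subject's stratum is known.

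About 3 to 4 revealed pairs come close to identifying a row, assuming 8 to 20 usable rows, one row per stratum and a known start. An unknown start would require more. Separately, 45% to 50% of assignments are certain once the first of the pair is known.

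The argument that arms emerge during recruitment assumes that unblinding follows each subject's own 12 weeks, which is how Section 13 reads, and that enrolment extends well beyond the first 12 weeks. No misuse is suggested, and the size of any resulting bias cannot be estimated from the documents.

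**What to change.** In the randomization paragraph of Section 13:

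- Replace the published table with a computer-generated stratified list from an undisclosed seed, using undisclosed varying block sizes (for example 2 and 4). Changing the source alone would leave the second of each pair predictable.
- Name the no-contact UCLA staff member who programs the devices as holder of the list. Release one assignment at a time, only after consent and the baseline CAPS-5 that sets the stratum are recorded.
- Keep N, the 1:1 ratio, the eight strata and the ANOVA. Make the permutation test follow the new blocks.
- Reconcile the timing. Section 13 has devices programmed before the baseline visit but randomizes after the baseline assessment. It describes two baseline visits, so it should say which is meant.

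The cost is a short program and a few sentences, using a role already in the plan. The downside is slightly more possible imbalance at the end of strata. A stratum stopping inside a block of four can be off by two rather than one, so the extreme difference is 8 × 2 = 16 (45/29) instead of 8 (41/33). Varying blocks reduce predictability within a block but do not abolish it, so custody and the release step matter as much as the list.

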This is a collaboration between the VA GLA and UCLA. All study activites will will be performed at the VA Greater Los Angeles or UCLA as determined by the Principal Investigator, in consultation with the PTSD Clinic and Domiciliary Care Program directors, as well as the subject's preference. Identification, recruitment and consenting of subjects for participation will be performed at the VA GLA PTSD Clinic or the Domiciliary Care Program. The baseline visit, Week 4 visit, and Week 8 visit will be conducted at the VA GLA PTSD Clinic or Domicialiary Care program without exception. All other study activities and visits will be performed at UCLA, or at the VA GLA PTSD Clinic or Domiciliary Care Program. If subjects prefer that visits be performed at the VA, the clinic director approves such visits, and space is available in the clinic, these visits will be performed at the VA GLA PTSD Clinic or the Domiciliary Care Program. Subjects will be randomized to treatment with either active or sham TNS for a period of eight weeks. Subjects will be randomly assigned in a double-blind manner (n=37 in each group); all subjects and the research staff who interact with them will be blinded to assignment, and a separate UCLA staff member of the research team who has no contact with subjects will program the TNS device settings. Subjects assigned to the sham treatment condition will receive a TNS stimulator that will look identical to the active treatment stimulator, and will follow identical procedures for the use of this stimulator. The sham unit, however, will deliver no actual nerve stimulation (i.e., it will pulse at 0 Hz). It will be explained to all subjects that they may or may not feel any sensation while using the device and any sensations or lack there of is not indicative of which treatment they are receiving. There is no noise associated with the device. The TNS device is equipped with a lighted display which will turn on to indicate to the patient when stimulation is being administered. The display on the sham device will turn on when stimulation is given at 0 Hz to avoid the appearance of a difference between the sham and active treatment.

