Subjects will be followed weekly with ratings of PTSD symptoms, mood and anxiety, as well as examinations for risk of suicidality. Week 8 endpoint measures will include severity and frequency of PTSD symptoms, quality of sleep, and quality of life measures. The primary endpoint measure is the change in symptom severity at the week 8 visit. The week 8 time point will be used to compare changes in symptoms between subjects who were randomly assigned to the active vs. sham TNS treatment condition. Subjects also will be interviewed an additional 4 weeks after the conclusion of the sham controlled treatment, and their mood and anxiety symptoms assessed, to examine the durability of any symptom change that subjects experienced during the initial 8 weeks. At the end of week 8, subject improvement will be assessed and those showing a $\geq 25\%$ improvement from baseline at the end of 8 weeks of treatment will be eligible to participate in the 42-month extension phase to monitor and observe possible benefits of prolonged TNS in responders. Subjects who participate in the extension phase will remain blinded. Subjects complete the PCL-M and BDI monthly during their participation in the extension phase. The PCL-M monthly score determines on-going inclusion in this phase. Subjects will be withdrawn in the case of adverse events, or symptom worsening (quantified as > 25%worsening in symptoms after one month as compared to the beginning of the extension phase as assessed using the PCL-M total score). Subjects way also voluntarily withdraw from the extension phase at any time.

Subjects who do not participate in the extension phase will be unblinded and told whether they received the active or sham-controlled treatment after all study and follow-up visits have been completed. This includes completion of the eight-week double-blind treatment phase and four-week follow-up phase for a total of 12 weeks in this study. Data will be examined for differences

between active and sham treatment, as well as safety and acceptability of the treatment. If positive, this preliminary study will serve as the basis for a larger pivotal trial of effectiveness.

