Screening Procedures and Instruments: After signing the consent form, the research coordinator will interview subjects to ask about demographic data and assess for possible exclusion criteria. The instruments listed below will be used to determine eligibility for the study and assess symptom severity. Instruments will be administered on the schedule shown in Table 1 below. Clinician-Administered PTSD Scale for DSM-V (CAPS-5-5) (Blake et al., 1995; Weathers et al., 2001): The CAPS-5 will be used both to establish eligibility for inclusion in the protocol and as an outcome measure. This 30-item structured interview assesses the presence, frequency, and severity of symptoms of PTSD. It provides a continuous score of frequency and severity for each symptom, with overall severity characterized by summing the total score for the individual items. The CAPS-5 has good psychometric properties across a wide variety of clinical populations and research settings (Weathers et al., 2001). We first will determine using the CAPS-5-5 whether the subject has at least one Criterion A stressor related to warzone exposure. If the subject meets this criterion, the remainder of the CAPS-5-5 will be administered to confirm the presence of PTSD and assess severity. Frequency and severity of symptoms are rated separately on a 0-4 scale.

Mini International Neuropsychiatric Interview for DSM-IV, Version 5.0 (MINI) (Sheehan et al.,1998): The MINI is a short yet accurate structured diagnostic interview used to diagnose current and lifetime Axis I disorders according to DSM-IV criteria. The assessment takes approximately 15 minutes to administer (Sheehan et al., 1998) We will specifically assess current substance dependence, current and/or history of psychosis, bipolar disorder, and to assess possible presence of exclusion criteria through use of relevant modules from the MINI. We also will utilize this instrument to determine the presence of Major Depressive Disorder (MDD); subjects will not be ruled-out because of the presence of MDD, but the presence of the illness will be used as a covariate. If presence of MDD appears to affect outcome, we may perform a subgroup analysis in subjects with comorbid MDD.

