Safety and Compliance: Assessment will be performed by the research coordinator to assure the device is being used safely and as directed.

Assessment instruments will be administered by the study coordinator ([name], R.N., [name] and [name]). [name] has over 20 years experience in assessment of psychiatric patients in clinical trials. She will undergo standardized refresher training in conducting the MINI interview, and in administering or supervising completion of the instruments utilized in this study. She will undergo training in administering the CAPS-5 through the Trauma Psychiatry Program at UCLA ([name]., Director). Training will include practice interviews and feedback from trainers designed to calibrate to a consistent acceptable standard of administration.

TNS stimulation procedure. TNS will be performed using a CE-mark approved neurostimulator, the Monarch eTNS SystemTM (NeuroSigma, Inc., Los Angeles CA); in August 2012, NeuroSigma received CE mark certification for use of the Monarch for adjunctive treatment in epilepsy and MDD in adults and children age 9 and older. The Monarch comprises two elements: the electrical pulse generator and the hypoallergenic, self-adhering custom electrodes for delivery of the signal to the supraorbital and supratrochlear branches of the V1 division of the trigeminal nerve. The system offers features not available in off-the-shelf transcutaneous nerve stimulators, such as limiting the applied current to known safe ranges and two levels of lock-out codes to prevent the device from being used by others or reprogrammed by the subject. As well, the composition and geometry of the electrodes has been engineered to provide the optimal amount of adhesion to be worn for 7-9 hours with a gel devoid of volatile compounds that are present in most surface electrodes used for nerve stimulation and that lead to skin irritation.

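### Fixed blocks of two, with arms disclosed subject by subject during the trial, create an avoidable route to unblinding of the CAPS-5 rater

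*Combined protocol and SAP*

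**What the plan says.** - **Allocation** (section 13, Conduct of the study). There are eight strata: gender, CAPS-5 below 78 or not, and current medication or not. Within each, blocks are fixed at two. The first of a pair is assigned from a random-number table; for the second, "If the first subject was assigned the active intervention, then the next subject would be assigned the sham, and vice versa".
- **Disclosure** (section 13, Overview, repeated under Conduct of the study). "Subjects who do not participate in the extension phase will be unblinded and told whether they received the active or sham-controlled treatment", once all study and follow-up visits are done. The Overview adds: "This includes completion of the eight-week double-blind treatment phase and four-week follow-up phase for a total of 12 weeks in this study". Extension participants stay blinded.
- **Trial length** (section 7). The trial phase lasts 36 months.
- **Blinding** (section 13, Overview). "all subjects and the research staff who interact with them will be blinded to assignment". Programming of the devices is given to another UCLA team member, who does not meet subjects.
- **Who rates** (section 13). At screening, "the research coordinator will interview subjects to ask about demographic data and assess for possible exclusion criteria". After the schedule tables: "Assessment instruments will be administered by the study coordinator". The coordinator also sees subjects at the weekly visits.
- **Primary endpoint** (section 13, Overview). "The primary endpoint measure is the change in symptom severity at the week 8 visit". The available text names no scale for it.
- **Clinic summaries** (section 13, Conduct of the study). With permission, clinic staff receive a summary of each subject's results. Whether it states the arm is not said.

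**The concern.** With fixed pairs, one known arm moves the partner's arm from an even chance to certainty. The rule is printed in the protocol, and the coordinator sees all three stratum factors. Disclosure at each subject's own 12 weeks releases arms while partners are still waiting for their week-8 rating.

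The CAPS-5 is an interview, so a rater who knows the arm may shift the score, perhaps without intending to. The PCL is self-report and much less exposed. If the primary scale is the CAPS-5, any such shift would bias the primary comparison toward the rater's expectation and raise the type I error.

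**Working it through.** **1. The plan's own figures.** 8 + 4 = 12 weeks; 74/2 = 37 per arm; 2 x 2 x 2 = 8 strata; digits 5-9 out of ten give probability 0.5 for the first of a pair. All reproduce.

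**2. What one told arm reveals.** In a permuted block of size b, one known arm lets another member's arm be named correctly with probability (b/2)/(b - 1). That is 1.00 for b = 2, 0.67 for b = 4 and 0.60 for b = 6.

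**3. When it matters for week 8.** The first of a pair is told at week 12 and the partner is rated at week 8. The rating follows the disclosure only if the partner was randomized more than 12 - 8 = 4 weeks later.

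**4. How many assignments are exposed.** The documents give no accrual pattern, stratum mix or extension uptake, so these are assumptions: uniform accrual, 10% women, 75% medicated, 50% at CAPS-5 78 or more, 30% entering the extension. Accrual is varied from 18 to 33 months. The upper end is the longest that fits: 36 months less about 3 for the last subject's 12 weeks. Simulation of 74 arrivals gives about 35 complete pairs. The last two columns suppose that **every** told arm reaches the partner's rater together with stratum and order.

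| Accrual | Pairs with gap over 4 weeks | First member told (x 0.70), simulated | Share of 74 |
|---|---|---|---|
| 18 months | 13.6 | 9.6 | 13% |
| 24 months | 16.9 | 11.9 | 16% |
| 33 months | 20.4 | 14.3 | 19% |

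Varying women over 5-20% and extension entry over 0-60% as well widens the full-leakage range to 4.2-22.5. The floor is 0.

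**5. Effect on the test.** Suppose a rater who knows the arm shifts the score by s SD in the expected direction. With k known assignments split evenly over the arms, the bias in the mean difference is (k/74) x 2s. The standard error is sqrt(2/37) = 0.2325 SD. Error degrees of freedom are taken as 74 - 8 - 1 = 65, with a two-sided 5% test (assumed; the available text states no alpha). Type I error comes from the noncentral t distribution.

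At s = 0.25 SD:
- k = 9.6: bias 0.065 SD, noncentrality 0.065/0.2325 = 0.28, type I error 5.9%.
- k = 11.9: bias 0.080 SD, noncentrality 0.35, type I error 6.3%.
- k = 14.3: bias 0.097 SD, noncentrality 0.42, type I error 6.9%.

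Partial leakage, 33-month accrual:

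| Share of told arms reaching the rater | Known | 0.25 SD | 0.5 SD |
|---|---|---|---|
| 10% | 1.4 | 5.0% | 5.1% |
| 25% | 3.6 | 5.1% | 5.5% |
| 50% | 7.1 | 5.5% | 6.9% |
| 100% | 14.3 | 6.9% | 13.0% |

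At 0.1 SD it never exceeds 5.3%. Section 13 lists three people in the coordinator role. If each knew only their own subjects, usable leakage would be about a third: 4.7 known, and 5.2% at 0.25 SD.

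**The case against.** The strongest reply is that no failure is shown. Harm needs a chain: disclosure subject by subject, the arm reaching a rater despite the stated blinding, the rater knowing stratum and order, a gap over 4 weeks, a first member outside the extension, a score shift, and the CAPS-5 as primary scale. Told subjects have no scheduled visit left after the week-12 interview. All of this stands, and it is why the counts are ceilings and not estimates.

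A reader might go further and infer that the plan has nobody able to disclose without breaking the blind. The documents do not support that. The device programmer has no contact with subjects, but could disclose by letter. Nor can a missing discloser or list holder be asserted: the part of section 9 on institutional roles, between sub-items (c) and (i), was not in the text available for this review and may assign those duties.

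The disclosure wording could also mean the last visit of the whole trial. The problem would then not arise for the main study, and the sentence should say so. A 12-week total fits one subject's schedule better.

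Prompt disclosure also has value to participants. That is a real cost of the change and is counted under the fix.

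**Conclusion.** The concern holds as a design weakness that can be removed at modest cost. Fixed pairs make a partner's arm certain once one arm is known, and the most natural reading of the disclosure rule releases arms while partners are still being rated.

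The ceiling is about 10 to 14 of 74 assignments (18 to 33 months' accrual), or a type I error of about 5.9-6.9%. This rests on the assumed stratum mix, 30% extension entry, every told arm leaking, a 0.25 SD shift and the CAPS-5 as primary scale. At 50% leakage or less and the same shift, the error is at most about 5.5%; only a larger assumed shift makes partial leakage matter more. The upper figure uses the longest accrual considered and should not be read as a typical case.

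A reader might infer that the trial's blind is broken or its result biased. The documents show neither. They state the intent to blind contact staff, and no section describes a coordinator learning a told arm.

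**What to change.** 1. **Disclosure timing** (section 13, Overview and Conduct of the study). State that routine disclosure takes place only after the last subject's week-12 visit and main-study data lock, by a named role that neither rates nor refers subjects. Keep the arm out of clinic summaries until then. Unblinding for safety is unaffected. This closes the route for the main study at any block size.
2. **Backstop** (section 13, Conduct of the study). Replace the fixed pairs with a concealed, computer-generated list of randomly varying block sizes (for example 2 and 4) in the same strata, and run the planned permutation test under that scheme. With step 1 in place the added gain is small. In simulation with every earlier arm in the stratum known, certain assignments fall from 35 to about 7, but correct guesses only from 74% to about 70%.

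**Cost.** Step 1 is a few sentences. With uniform accrual over T months, the mean extra wait for subjects outside the extension is T/2, that is 18/2 = 9 to 33/2 = 16.5 months. The share waiting more than 6 extra months is (T - 6)/T, that is 12/18 = 67% to 27/33 = 82%. A Domiciliary stay is typically 5-6 months (section 10), so many of those subjects would have to be re-contacted by letter or phone after leaving, and some may not be reached. Step 2 loosens arm balance slightly: the SD of the arm-size difference rises from about 2.0 to 2.3-2.4 subjects.
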